#### **6.5.2 Blinding Implementation and Protection**

Subjects and evaluators are blinded according to the protocol.

Randomization results will be kept confidential to the subjects in general. Randomization results are not reflected in inpatient history and other subject access documents. During and after the examination, study personnel should take care not to talk to the subject about the results of the randomization to avoid unnecessary unblinding

The assessors are blinded, and the data analysis team and pathologists could not obtain the randomization results from the medical history data.

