Study Process:	
1. Subjects meeting all inclusion criteria and those failing all exclusion criteria were included in the study before colonoscopy;
 
2. Include qualified novice doctors for colonoscopy training
 
3. Patients who met the requirements were enrolled and randomly assigned as follows
 
The experimental group: received painless colonoscopy training with the assistance of the artificial intelligence assistant system, which could prompt abnormal lesions and real-time withdrawal speed, and feedback the overspeed percentage.
 
Control group: routine painless enteroscopy training, no special tips.
 
4. After colonoscopy, the teacher scored the colonoscopy using ACE scoring scale

Security	Safety incidents shall be evaluated and reported according to the quality management measures for clinical trials of medical devices

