## **4 Endpoints**

### **4.1 Primary Endpoint**

- 1) CUSUM learning curve for colonoscopy (ACE scoring scale)
- 2) Average test score difference before and after training

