### **6.5 Randomization and Blinding**

#### **6.5.1 Randomization Implementation**

Randomization is conducted according to the study protocol, and the random contents are implemented in an electronic system block-randomized manner (n = 4; experimental group/control group = 1). Randomization prior to Colonoscopy to decide whether to use EndoAngel. The researchers randomized the random results generated by the electronic system, and the generated random results were stored in the research center. The random time (accurate to minute), random person, subject number and acronym were recorded in the corresponding positions of the electronic system.

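### Section 6.5.2 claims blinded evaluators without qualification, but no masking is described for the teacher, the only rater named for the ACE score

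*Combined protocol and SAP*

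**What the plan says.** Section 6.5.2 makes a general claim, "Subjects and evaluators are blinded according to the protocol", and later adds: "The assessors are blinded, and the data analysis team and pathologists could not obtain the randomization results from the medical history data". Neither evaluators nor assessors are defined there or in Section 6.5.3, which uses both terms again. The measures given are that "Randomization results are not reflected in inpatient history and other subject access documents" and that staff should avoid discussing the allocation with the patient.

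On the intervention, Section 6.5.1 says: "Randomization prior to Colonoscopy to decide whether to use EndoAngel". The Summary (Section 1, Study Process) describes the experimental arm as training with a system "which could prompt abnormal lesions and real-time withdrawal speed, and feedback the overspeed percentage". The other arm is described as "Control group: routine painless enteroscopy training, no special tips".

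On the rating, the same part of the Summary says: "After colonoscopy, the teacher scored the colonoscopy using ACE scoring scale". Section 6.3.3 repeats this, directly after the item stating that the trainee examines the patient with a teacher guiding. No other ACE rater is named anywhere. Section 4.1 makes the CUSUM learning curve based on ACE the first of two primary endpoints, and Section 8.3 sizes the trial on cognitive and motor score differences.

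**The concern.** ACE is a judgement made by a person. If that person knows whether the trainee had AI help, expectation may enter the score. It could favour EndoAngel, or it could work against it, for example if the teacher marks down a trainee who was prompted. Masking is the usual protection, and Section 6.5.2 reads as though it is in place.

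What is at stake is how the first primary result may be read. A difference in ACE-based learning curves carries more weight as a blinded assessment than as the opinion of a supervisor who knew the arm. With the general claim left as it stands, a report could present the result in the stronger form although the plan describes nothing that would justify it.

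**Working it through.** The plan has no figure for blinding to reproduce, so the check sets the sections against each other.

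1. **Who rates ACE?** The teacher (Section 1, Study Process; Section 6.3.3, item 4). No second or independent rater appears.
2. **Where is the teacher during the examination?** Guiding the trainee (Section 6.3.3, item 3). Items 3 and 4 both refer to the teacher without distinguishing two people. That they are the same person is the natural reading, but it is not stated.
3. **Is the allocation visible in the room?** The arms differ by live lesion prompts and a real-time speed display (Section 1). Someone guiding the procedure would be expected to notice them. No section says outright that the teacher sees the display, and the flow chart in Section 1.2 is not in the text available for review.
4. **Which safeguards reach the teacher?**

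| Safeguard | Section | Who it protects | Masks the ACE rater? |
|---|---|---|---|
| Allocation kept out of the inpatient history and documents open to the patient | 6.5.2 | Patient, users of the record | No |
| Allocation not discussed with the patient | 6.5.2 | Patient | No |
| Allocation not obtainable from medical history data | 6.5.2 | Data analysis team, pathologists | No |
| Sham or hidden display | none described | – | – |
| Masked second rater or masked scoring from video | none described | – | – |

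Images and video are collected, but the purpose given in Section 6.3.4 is to assess how EndoAngel functions, not to score ACE.

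5. **How does the plan define unblinding?** Section 6.5.3 counts showing the allocation to an evaluator as breaking the blind, and says that any leak would matter considerably for the analysis. If the teacher is an evaluator and sees the prompts, that happens at every experimental-arm examination.
6. **What depends on the rating?** From Section 8.3:
   - Motor: 2.59 − 2.38 = 0.21 points; 0.21 / 2.38 = 8.8% of baseline; 350 cases.
   - Cognitive: 2.8 − 2.5 = 0.30 points; 0.30 / 2.5 = 12.0% of baseline; 126 cases.
   - Enrolment: 350 × 1.10 = 385, the plan's stated total, so it follows from the motor score.

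These differences give the scale on which a rating shift would count. They say nothing about whether a shift would occur. Section 8.2 names no test for ACE, and the plan states no standard deviation, significance level or power, so an effect on the error rate cannot be derived from the documents.

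**The case against.** The strongest reply is that Section 6.5.2 can be read narrowly. The sentence that calls the assessors blinded goes on to name the data analysis team and pathologists. If those two groups are the evaluators meant, the statement is correct and nothing contradicts it. That reading is possible, and for this reason a direct contradiction is not established. It does not remove the problem. The sentence lists the assessors alongside the other two groups, as if separate from them, and the opening claim has no limit. Even on the narrow reading, the first primary endpoint is rated without described masking and the plan does not say so.

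A second reply is that the case rests on two inferences: that one teacher both guides and scores, and that this teacher can see the display. Both are likely from Section 6.3.3, but neither is stated. Section 7.1 also refers some evaluations to the CRF, which is not available here. This stands as a limit on confidence.

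Third, a supervisor who sees the examination is largely inherent in supervised training. That is fair, and it is a reason to describe the rating accurately, not to demand masking of a live supervisor. Measures the teacher does not rate, such as overspeed percentage and pathology-based detection, give context but cannot show that ACE scores are free of expectation.

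Finally, correcting the wording does not reduce bias. That is true. Masked scoring from the recordings might, but the documents do not say whether the recordings show the AI overlay, so it is not proposed here.

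**Conclusion.** The blinding claim in Section 6.5.2 is not supported for the ACE score as the plan is written. The only named rater works where the allocation would be expected to be visible, and none of the described safeguards masks that person. Rater expectation, in either direction, therefore cannot be excluded as an explanation of an ACE/CUSUM difference, where the planned differences are 0.21 and 0.30 points.

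The conclusion assumes that the guiding and scoring teacher are the same person, that this person can see the prompts, and that no masking procedure exists outside the text available.

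A reader might infer more: that the ACE scores are biased, that the false-positive rate is raised by a known amount, or that the whole primary analysis is compromised. The documents support none of these. The size and direction of any shift are unknown. An error rate would need a spread, a test, independence between cases and a shift, none of which the plan states, and a comparison of means is not the CUSUM endpoint. The second primary endpoint, the test score difference before and after training, has no stated scorer, and this point does not extend to it.

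**What to change.** In Section 6.5.2, replace the general statement with one that limits blinding to patients, pathologists and the data analysis team. Then state the position of the ACE rater. If a masking procedure for that person already exists, describe it. If not, say that ACE scoring is unblinded, and that the ACE/CUSUM result will be reported and interpreted as an open-label subjective rating.

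The cost is a wording correction and a sentence on reporting, with no change to procedures, staff or sample size. The downside is that the trial gives up the claim of blinded assessment for ACE. The change does not itself reduce rating bias; it stops the result from being read as a blinded assessment.

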### **6.5.3 Unblinding**

Uncovering or breaking the blindness means displaying the randomized results to the subjects or evaluators. Researchers should protect the blind method as far as possible. Uncovering the randomized results of a single subject may lead to the leakage of the randomized results of other subjects. Any leakage of the randomized results will have a significant impact on statistical analysis. In general, it is prudent to deal with the disclosure of blind law. In the following cases, it is possible to consider the disclosure of blind law:

- 1) endangering the safety of subjects: For example, in some serious adverse events, subjects need to know the randomized results to inform other physicians to take appropriate emergency treatment.
- 2) Threatening the safety of the assessor: When the assessor is facing potential safety hazards, he needs to know the randomization results.
- 3) Compliance: For reasons of partial compliance, in certain circumstances, if the research instruments and cases involved in unexpected adverse events are needed, the results of randomization should be made public to the relevant departments or the public.
- 5) Other management reasons.

### **6.6 Concomitant therapy and medication**

The concomitant treatment and concomitant medication were recorded from the time the subject signed the informed consent to the time the study was completed. Concomitant treatment and concomitant medication should be recorded in the CRF, or a clear copy of the form available from the research center should be kept in the CRF as research data to identify other factors affecting the end of the study. When recording the concomitant treatment and concomitant medication, the indications and the starting and ending time of use should be clearly defined, and the corresponding types of adverse events should be indicated for the treatment measures to cope with adverse events. When using a copy of the study center form, the investigator should sign the copy and indicate the date of review to confirm that the document is a study document.

## **7 Basis of study protocol and risk/benefit analysis**

EndoAngel is used to provide assistant to monitor the operation of endoscopists, which will not provide diagnosis. Doctors make their own diagnosis on the basis of EndoAngel's results. The security of the software and the improvement of endoscopic physician's diagnosis and treatment level have also been confirmed in the previous feasibility study. And the patients in this study carry out the diagnosis and treatment according to the conventional treatment measures, which are formulated in accordance with the standard medical treatment procedures and do not increase the risk of the subjects.

### **7.1 Selection of endpoints**

The primary endpoints are:1) the CUSUM learning curve for colonoscopy (ACE scoring scale); 2) the average test score difference before and after training.

The secondary endpoints are: 1)Detection rate of advanced adenoma;2)Polyp Detection Rate, PDR;3)Average number of adenomas detected per patient;4)The detection rate of large, small and micro polyps;5)The average number of large, small and micro polyps detected; 6)The detection rate of large, small and micro adenomas;7)The average number of large, small and micro adenomas detected;8)The detection rate of adenoma in different sites;9)The average number of adenomas detected in different sites;10)Number of missed return of the sliding endoscopy/number of successful return of the sliding endoscopy;11)Real-time gut cleanliness score;12)Withdraw overspeed percentage;13)The withdraw time;14)Ratio of ileocecal reach

Adverse events in safety indicators shall be judged in accordance with relevant regulations, and serious adverse events shall be recorded and reported in accordance with regulations.

Other evaluations are detailed in the Case Report Form (CRF).

### **7.2 Definition of participants**

Patients were included according to the indications and contraindications described in the use plan. Because of practical reasons (such as younger patients, participation in a number of clinical studies, alcohol/drug dependence patients, and other factors that may affect the completion and/or reliability of gastroscopy) and ethical reasons (whether informed consent can be completed, etc.), the entry and discharge criteria have been reduced.

### **7.3 Adverse events**

The relevant definitions of adverse events are as follows:

Adverse Events (AE): Any adverse medical event, unexpected disease or injury, or adverse clinical manifestations (including abnormal laboratory findings) that occur in a subject, user or other person, whether or not associated with medical devices.

Serious Adverse Events (SAE): Adverse Events with the following information:

- causing death.
- leading to severe deterioration of the health of the subjects, including
- leading to life-threatening diseases or injuries,
- Causing impairment of body structure or function.
- Need hospitalization or extended hospitalization
- lead to hospitalization and preventive medical or surgical intervention
- Permanent damage to body structure or function
- Fetal distress, fetal death or congenital abnormalities or congenital defects.

Note: Hospitalization for existing conditions, or surgery required in the program, without serious deterioration of health status, is not considered a serious adverse event. Purposeful hospitalization, such as economic or reimbursement reasons, is not considered a serious adverse event.

Unexpected adverse device response (UADE): refers to adverse events related to medical devices that were not previously identified in the current version of the risk analysis report in terms of nature, severity or incidence. The definition includes any event caused by insufficient or inadequate description of the use or deployment of the device. This definition includes any event caused by a user's error.

#### **7.4 Expected and trial-related adverse events**

Previous studies have shown that the expected adverse events are basically the same as the complications of conventional endoscopic diagnosis and treatment.

The instrument used in this experiment is a medical software which is not in contact with human body. There is no difference between the experimental operation and the routine operation. The intervention measures (such as randomized process) in the experiment may slightly increase the incidents of diagnosis and treatment.

#### **7.5 Risk minimization**

In this study, when there are bugs in the software, doctors can still operate under their own judgment without affecting conventional diagnostic and treatment measures, greatly reducing the risk of the test.

## 7.6 Related benefits

According to the results of previous multi-center randomized controlled trials, it has been proved that EndoAngel can improve the examination quality of colonoscopists. In this observational study, subjects receiving EndoAngel assisted colonoscopy may obtain higher quality colonoscopy due to the subject effect of colonoscopists.

## 7.7 Overall feasibility analysis

EndoAngel is an independent system including both software and computer hardware, which can monitor image data 24 hours a day. The system is not invasive. The overall operability is strong.

# 8 Statistical Analysis

## 8.1 Statistical Analysis Plan

Data management and statistical analysis were implemented by Renmin Hospital of Wuhan University.

## 8.2 Methods

Continuous variables should be described by number of subjects, mean, standard deviation, median, minimum and maximum. The classification variables are summarized by frequency and percentage.

Spearman rank correlation analysis was used to analyze the correlation between endoscopic overspeed percentage / intestinal preparation score and adenoma detection rate / advanced adenoma detection rate / polyp detection rate.

Univariate analysis was used to analyze the correlation between the number of unreturned slides/returned slides and the detection rate of adenoma/late adenoma/polyp.

Chi-square analysis was used to analyze the detection rate of adenomas in different scores of intestinal segments.

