## 1.2 Flow chart

## 2 Introduction

Endoscopic diagnosis and treatment play an important role in the discovery and treatment of digestive tract diseases. Common endoscopic examination includes gastroscopy, colonoscopy, enteroscopy, capsule endoscopy, ultrasound gastroscopy, endoscopic retrograde cholangiopancreatography and other related techniques, which can be used in the diagnosis and follow-up of early gastric cancer, peptic ulcer, esophageal varices, precancerous lesions, intestinal polyps, intestinal adenomas, bowel cancer lesions, inflammatory bowel diseases, pancreatic diseases, biliary diseases, etc. At present, digestive endoscopy almost covers the diagnosis of most diseases of the digestive tract, and the digestive system diseases that can not be seen in the direct visual field of endoscope can also be realized by the related techniques based on ultrasound endoscopy, ERCP and other endoscopy (we call endoscopy here), so as to achieve the coverage of the whole digestive system. It can be seen that digestive endoscopy is of great significance for the diagnosis and development of digestive system diseases. At present, the demand for endoscopic examination in China is high, and the supply of endoscopic surgery in hospitals is short of supply, which puts forward high requirements for the proficiency and accuracy of operation doctors.

In recent years, deep learning has developed rapidly in the field of medicine. Andre Esteva et al. used deep neural networks (DNN) to classify skin cancer to an expert level. Our previous experiments show that deep learning has high accuracy in endoscopic quality monitoring, which can effectively standardize the operation of doctors, reduce the blind area of examination, and improve the quality of endoscopic examination. At the same time, it can also monitor the doctor's withdrawal time and improve the detection rate of adenoma. in the previous work of our group, we have successfully developed a deep learning-based enteroscopy speed monitoring, intestinal cleanliness evaluation, and in clinical trials to verify the effectiveness of artificial intelligence model in improving the quality of gastroscopy, enteroscopy.

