### **6.3.4 Post-operative Managements**

[figure not shown]
- 1) Postoperative routine nursing
- 2) The anesthetized subjects were observed until they woke up
- 3) Patients with no lesions such as polyps were followed up until they woke up and left

the endoscopic room.

- 4) Clinical information such as the examining physician, duration of examination, sedation status, whether to ileocecal reach, bowel readiness, complications, polyp characteristics (number, location, size, color, and shape), and pathological results will be collected and recorded in a Web-based data management system.
- 5) The images and video data were collected for the functional evaluation of EndoAngel, such as the withdrawal speed, the number of sliding not returned/sliding returned, real-time intestinal preparation score, polyp detection and typing, etc.

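### The planned overspeed–detection correlation names no arm, trainee or unit of analysis, so pooling the arms could produce a link that exists in neither

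*Combined protocol and SAP*

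**What the plan says.** Section 8.2 (Methods) names two association analyses of detection. The first reads: "Spearman rank correlation analysis was used to analyze the correlation between endoscopic overspeed percentage / intestinal preparation score and adenoma detection rate". The sentence goes on to advanced adenoma and polyp detection. The second reads: "Univariate analysis was used to analyze the correlation between the number of unreturned slides/returned slides and the detection rate of adenoma/late adenoma/polyp". Neither sentence mentions arm, trainee, hospital, analysis set or unit of analysis, and no other section supplies these for the two analyses. Section 8.4 assigns its analysis sets to the primary efficacy endpoints only.

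The Summary (Study Process) describes the AI system in the experimental arm as one "which could prompt abnormal lesions and real-time withdrawal speed, and feedback the overspeed percentage". For the other arm it says: "Control group: routine painless enteroscopy training, no special tips". The Introduction states of the underlying technology that "it can also monitor the doctor's withdrawal time and improve the detection rate of adenoma".

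Section 4.2 defines overspeed percentage for a single withdrawal, but defines detection rates as patients with a finding divided by all patients examined.

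**The concern.** The intervention acts on both sides of the overspeed correlation. It shows withdrawal speed and overspeed, which may lower the overspeed percentage, and it prompts lesions, which may raise detection. Arm is then a common cause. If the AI arm has less overspeed and more detection, the combined data will show less overspeed going with more detection, even if speed and detection are unrelated among AI cases and among control cases. The report could then say that slower withdrawal finds more adenomas when the data show only that the AI arm had both.

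Two further gaps apply to all three predictors (overspeed, preparation score, slide returns). First, a detection rate exists only for a group, while each predictor is measured per examination, so the analysis cannot be run until a unit is chosen. Second, trainees perform repeated cases. If the case is the unit, a plain Spearman test treats those cases as independent.

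**Working it through.** **The plan's own figure.** Section 8.3 gives no sample size for these analyses. Its total reproduces as 350 × 1.10 = 385, and 385 is used below.

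**Inputs from the documents.** N = 385 (8.3); 1:1 allocation (6.5.1); AI feedback on both lesions and speed in one arm only (Summary).

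**Inputs assumed, because the documents give none.** Detection in control v AI of 20% v 25%, 20% v 30% and 15% v 30%; overspeed lowered by d = 0.5 or 1 SD in the AI arm; two-sided 5% test; the case as the unit; no overspeed–detection link within either arm.

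**Formula.** With equal arms and no within-arm link, the size of the pooled correlation is approximately the product of two correlations with arm:

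- arm with overspeed: a = d / √(d² + 4), which is 0.5/√4.25 = 0.243 or 1/√5 = 0.447;
- arm with detection: b = [(p₁ − p₀)/2] / √[p̄(1 − p̄)], which is 0.025/√(0.225 × 0.775) = 0.060, 0.05/√(0.25 × 0.75) = 0.115, or 0.075/√(0.225 × 0.775) = 0.180.

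The rejection rate is approximately Φ(−1.96 + λ) + Φ(−1.96 − λ), with λ = ab√384. The sign of the correlation is negative.

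**Results.** The last three columns come from 1,500 simulated trials per row.

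| Detection | d (SD) | ab | Rejection, formula | Mean rho, simulated | Rejection, pooled | Rejection, ranks within arm |
|---|---|---|---|---|---|---|
| 20% v 25% | 0.5 | 0.015 | 5.9% | −0.014 | 5.4% | 4.6% |
| 20% v 25% | 1.0 | 0.027 | 8.2% | −0.028 | 9.4% | 5.5% |
| 20% v 30% | 0.5 | 0.028 | 8.5% | −0.029 | 8.6% | 4.5% |
| 20% v 30% | 1.0 | 0.052 | 17.3% | −0.051 | 16.2% | 4.3% |
| 15% v 30% | 0.5 | 0.044 | 13.7% | −0.043 | 13.2% | 5.4% |
| 15% v 30% | 1.0 | 0.080 | 35.0% | −0.080 | 34.8% | 5.1% |

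Formula and simulation agree. Across every N = 385 setting simulated, ranking within arm kept rejection at 4.1% to 6.3%.

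**Both variables must move.** When the simulated AI changed at most one of the two, pooled rejection stayed at 3.7% to 6.0%. The arm artefact therefore depends on an AI effect on the predictor as well as on detection.

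**Which predictors qualify.** The Summary documents feedback on overspeed. It lists no prompt on slides; 6.3.4 mentions slide counts and preparation score only as data collected for functional evaluation ("such as the withdrawal speed, the number of sliding not returned/sliding returned, real-time intestinal preparation score"). Bowel preparation is routine and precedes the examination (6.3.2). The arm mechanism is documented for overspeed alone.

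**Trainee clustering.** The number of trainees is not given. The assumptions are 6, 10 or 20 trainees, a between-trainee SD of 0.6 for overspeed (in units of the within-trainee SD) and 0.5 on the log-odds of detection, overall detection near 25%, no arm effect and no within-trainee link. A plain Spearman test on 385 cases rejected in 10.5%, 8.5% and 7.3% of trials when the two trainee effects were unrelated, and in 19.3%, 19.9% and 18.6% when they correlated at −0.5.

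**The case against.** **Pooling is not stated.** Section 8.2 does not say that arms are combined or that cases are treated as independent. That stands: both are inferred from silence. But nothing restricts or stratifies the data, the second analysis is called univariate, and an analyst following the text would have no instruction to separate the arms.

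**The unit may not be the case.** The word rate allows an analysis by trainee or by period, and the case-level figures above would not then apply. This also stands, and it makes the missing unit a defect in its own right.

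**The size is assumed and small.** No detection rate, overspeed effect or alpha is given. At 20% v 25% with a 0.5 SD shift the artefact all but vanishes, and even in the worst setting about 65% of trials show nothing significant. This limits the claim to what can happen.

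**The link might be genuine.** If the AI raises detection by slowing withdrawal, the correlation is no artefact. A within-arm analysis can still detect such a link; the pooled one cannot tell the two explanations apart.

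**Stronger readings to avoid.** A reader might infer that the slide-return and preparation-score analyses are confounded by arm in the same way. The documents describe no AI effect on either, and without one the artefact does not arise. A reader might also infer that the randomised comparison is compromised. It is not: these analyses serve neither primary endpoint in 4.1 nor the purpose stated in 5.1.

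**Conclusion.** The concern holds for overspeed percentage. Section 8.2 omits arm, although the Summary shows that arm can affect both variables. If cases are pooled, the false-positive rate is about 5% to 35% against a nominal 5%, with an induced rho of at most about 0.08 in size. That range rests on assumed detection of 20% v 25% up to 15% v 30%, an overspeed shift of 0.5 to 1 SD, 385 cases, a two-sided 5% test and the case as the unit. A spurious link can appear; the documents do not show that it will.

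For slide returns and preparation score, only the undefined unit and the missing allowance for repeated cases per trainee stand. This is a minor improvement to secondary association analyses.

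**What to change.** Amend 8.2 to say that:

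- the patient is the unit and detection is yes/no for each of adenoma, advanced adenoma and polyp;
- the analysis set is named;
- the association is estimated within arm, by arm-stratified ranks or by a logistic model with arm as a covariate;
- repeated cases per trainee are allowed for by cluster-robust errors, or by a trainee effect if there are enough trainees to estimate one;
- estimates are reported with 95% confidence intervals.

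A full mixed model for every analysis is more than the defect needs. Stratified ranks alone brought the arm artefact back to about 5%, though they do not deal with clustering. Keep the model minimal for advanced adenoma, where events may be few.

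No new data are needed. Arm is known from randomisation (6.5.1), and 6.3.4 already records "Clinical information such as the examining physician, duration of examination, sedation status" along with polyp and pathology results. The cost is a change of SAP wording, a little more analysis work and somewhat wider intervals.
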